8.2. Setting

Clinical practice and treatment of each patient will follow as determined by each treating HCP individually. There will be no interference from Pfizer with the HCP's diagnostic and treatment decisions. The decision to treat a patient with lorlatinib will be prior to and independent of participation in the real world data collection and according to the clinical judgement of their HCP. Therefore, the data collection will in no way influence prescribing patterns or treatment decisions. If eligible, the patient will receive treatment through Pfizer's expanded access program independent of involvement in the collection of real world data.

HCPs treating a patient approved to receive lorlatinib via Pfizer's expanded access program will be invited to take part in the real world data collection. Upon HCP agreement, they will receive access to the EDC, where they can enter data into the DCT.

The first pediatric neuroblastoma patient received lorlatinib in March 2017 as part of expanded access programs and the program is ongoing. Data collection is anticipated to initiate in January 2021 and is estimated to have last patient entered into real world dataset at

PFIZER CONFIDENTIAL

the end in December 2023. Database lock would occur in February 2024, as outlined in [Section 5](#).

Data will be collected via DCT at multiple time points for patients who are receiving ongoing treatment. These timepoints will be determined by HCP standard practice for treatment and follow-up of their patients. Visits are anticipated to occur every 3-4 months, corresponding with re-supply of lorlatinib. Data will be collected on a continual basis until discontinuation of treatment with lorlatinib, death, loss to follow-up or end of study, whichever comes first.

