8.3. Variables

Variables will include demographics at the start of lorlatinib treatment (age, gender, race, body surface area (BSA)), clinical characteristics (date of initial diagnosis, high risk at diagnosis, ALK aberration date of sample collection and testing, testing platform, ALK and other genetic mutations, ALK amplification, translocation or over-expression, and MYCN amplification, prior anti-cancer treatment, ALK inhibitor use, disease status), treatment start date, starting dose, resupply date(s), BSA, response assessment (date, disease status, HCP reported response, International Neuroblastoma Response Criteria (INRC) response assessment criteria²⁸ and assessment modality), last date of lorlatinib, patient alive, date of death, date of discontinuation of lorlatinib and reason for discontinuation of lorlatinib. Safety data will be collected in DCT as outlined in [Section 10](#).

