8.7.3 Patient Disposition and Demography

Patient disposition will account for the number of patients receiving treatment, continued treatment and discontinued treatment at a specific milestone. Potential reasons for discontinuing treatment will include disease progression, adverse event excluding death, death, lost to follow up, and other.

Demographic and patient characteristics will include variables as noted in [Section 8.3](#). Additional variables will be statistically derived and reported including time since initial diagnosis. Time since initial diagnosis, in months, will be derived as: $12*((\text{Date of initial diagnosis}) - (\text{First Date of lorlatinib Treatment}) + 1) / 365.25$.

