8.7.5 Effectiveness endpoints

To assess the effectiveness of lorlatinib, the following endpoints will be collected via the DCT or derived:

Endpoint	Source Variable (if endpoint derived)	Description/Derivation
Objective tumor response of primary tumor (soft tissue), soft		Collected by the DCT at each visit. Outcomes include complete response (CR), partial response

PFIZER CONFIDENTIAL

tissue metastasis, and bone metastasis		(PR), stable disease (SD) and progressive disease (PD).												
Bone marrow response		Collected by the DCT at each visit. Outcomes include CR, PD, minimal disease (MD) and SD.												
HCP Reported Objective Response		Collected by the DCT at each visit. Outcomes include CR, PR, minor response (MR), SD and PD.												
Derived Objective Response	Objective Tumor response components	
Derived and compared for robustness to the HCP Reported Objective Response applying the following rules:
 
  
 RESPONSE	CRITERIA	
   
 Complete Response (CR)	All components meet criteria for CR	
 
 Partial Response (PR)	PR in at least one component and all other components are either CR, MD (Bone marrow), PR (Soft tissue or Bone) or Not involved (NI); no component with PD.	
 
 Minor Response (MR)	PR or CR in at least one component but at least one other component with SD; no component with PD.	
 
 Stable Disease (SD)	SD in one component with no better than SD or NI in any other component; no component with PD.	
 
 Progressive Disease (PD)	Any component with PD	
  
	RESPONSE	CRITERIA	Complete Response (CR)	All components meet criteria for CR	Partial Response (PR)	PR in at least one component and all other components are either CR, MD (Bone marrow), PR (Soft tissue or Bone) or Not involved (NI); no component with PD.	Minor Response (MR)	PR or CR in at least one component but at least one other component with SD; no component with PD.	Stable Disease (SD)	SD in one component with no better than SD or NI in any other component; no component with PD.	Progressive Disease (PD)	Any component with PD
RESPONSE	CRITERIA													
Complete Response (CR)	All components meet criteria for CR													

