Partial Response (PR)	PR in at least one component and all other components are either CR, MD (Bone marrow), PR (Soft tissue or Bone) or Not involved (NI); no component with PD.													
Minor Response (MR)	PR or CR in at least one component but at least one other component with SD; no component with PD.													
Stable Disease (SD)	SD in one component with no better than SD or NI in any other component; no component with PD.													
Progressive Disease (PD)	Any component with PD													
Best Overall response	HCP Reported Response	Derived as the best overall response taking the HCP Reported Response observed up to the data cut-off date for a specific milestone. (The												

PFIZER CONFIDENTIAL

	Repeated using Derived Objective Response	sequence order from best to worst is CR, PR, MR, SD, PD.)
Overall Response Rate (ORR)	Best Overall Response	Derived as Best overall response of CR+PR of the total population observed up to the data cut-off date for a specific milestone.
Duration of response	Treatment Start and HCP Reported Response Date	Derived as (Date of PD or death, whichever occurs first) – (Date of PR or CR, whichever occurs first) + 1
Progression free survival (PFS)	Treatment Start and HCP Reported PD/Death Date	Derived as (Date of PD or death (by any cause in the absence of PD)) – (Treatment start date) + 1
Duration of treatment	Treatment Start and Stop Dates	Derived as (Treatment stop date) – (Treatment start date) + 1
Overall survival (OS)	Treatment Start and Death Dates	Derived as (Date of death) – (Treatment start date) + 1

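### PFS and DOR have no rule for patients who stop lorlatinib for disease progression without a recorded PD assessment; following the source column would censor them informatively

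*Combined protocol and SAP*

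**What the plan says.** The endpoint table in Section 8.7.5 gives the PFS source variable as "Treatment Start and HCP Reported PD/Death Date" and the derivation as "Derived as (Date of PD or death (by any cause in the absence of PD)) – (Treatment start date) + 1". For DOR the source is "Treatment Start and HCP Reported Response Date" and the derivation is "Derived as (Date of PD or death, whichever occurs first) – (Date of PR or CR, whichever occurs first) + 1". In the same table, PD is a category of the HCP-reported objective response entered at each visit: "Outcomes include CR, PR, minor response (MR), SD and PD".

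Progression is also recorded in a second place. Section 8.3 collects "date of discontinuation of lorlatinib and reason for discontinuation of lorlatinib", and Section 8.7.3 states: "Potential reasons for discontinuing treatment will include disease progression, adverse event excluding death, death, lost to follow up, and other". That section concerns disposition, and nothing in 8.7.5 or 8.7.6 refers back to it.

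Section 8.7.6 censors PFS at last contact for patients with neither PD nor death by the cut-off. It censors DOR at the last visit for patients without symptoms of progression. Section 8.2 says that data on patients under ongoing treatment are collected "until discontinuation of treatment with lorlatinib, death, loss to follow-up or end of study, whichever comes first". Section 9.3 makes the discontinuation date the last visit date.

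**The concern.** Treatment can stop for progression without any visit response of PD having been entered. Visits follow local practice and are expected every 3-4 months (Section 8.2), so clinical deterioration between visits may end treatment before a formal assessment. Section 8.7.2 keeps every patient with data in the analysis whether or not eligibility is met. That can include patients with no post-dose tumour assessment, for whom the stop reason may be the only record of progression. Missing data are not imputed apart from partial dates (Section 8.7.8).

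If such a patient is treated as event-free, censoring happens because of the event being measured. Kaplan-Meier estimation assumes that censored patients carry the same future risk as those still followed, and here that fails in one direction. PFS and DOR both lengthen. The same report would list the patient as discontinued for progression in one table and as progression-free in another. DOR and PFS are named objectives (Section 7), and results may go to regulators and to publication (Section 11).

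**Working it through.** The plan gives no PFS, DOR or event-count figure to reproduce. The check is a reading of the rules followed by an illustration of size.

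**Reading the rules for one patient: stopped for progression, no PD response entered**

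| Step | Source column followed (8.7.5) | Censoring wording followed (8.7.6) |
|---|---|---|
| Is there a PFS event? | No, unless a death is recorded | Apparently yes: the patient has progressed |
| PFS date | Last contact, probably near the stop date because collection ends there (8.2) | No date rule given |
| Is there a DOR event (if a responder)? | No, unless a death is recorded | Apparently yes: progression is present |
| DOR date | Last visit, which is the stop date (8.2, 9.3) | No date rule given |

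Two programmers working carefully from the same data could therefore produce different curves.

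**Illustration of size under the left-hand column**

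Assumptions, none of them in the documents:
- PFS is exponential with true median 6 months, used as a scale.
- A share f of progressions is recorded only as the stop reason, with f = 10%, 20% or 30%.
- Those patients are censored permanently at the time of progression.
- All PFS events are progressions.

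Removing a random share f of events at their own times multiplies the hazard by (1 − f). Hence:
- apparent median = 6 / (1 − f)
- apparent 12-month PFS = 0.25^(1 − f), since 12 months is two true medians and true PFS there is 0.5² = 25%.

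| f | Apparent median (months) | Apparent 12-month PFS |
|---|---|---|
| 0 | 6.0 | 25% |
| 10% | 6/0.9 = 6.7 | 0.25^0.9 = 29% |
| 20% | 6/0.8 = 7.5 | 0.25^0.8 = 33% |
| 30% | 6/0.7 = 8.6 | 0.25^0.7 = 38% |

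A simulation checked the algebra: 3,000 runs, N = 50 (the maximum in Section 8.1), uniform 0-24 month administrative censoring. The typical Kaplan-Meier median was 6.0, 6.6, 7.5 and 8.7 months for f = 0, 10%, 20% and 30%. Mean events fell from 33 to 23. Under the same assumptions the factor 1/(1 − f) applies to median DOR.

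**The case against.** A reader might infer that the plan counts PD assessments and nothing else, and that it prescribes censoring for these patients. The documents do not support that. The PFS source refers to HCP-reported PD, and the HCP also enters the reason for stopping, so the phrase can include it. The wording in 8.7.6 does not describe a patient who stopped for progression. What the plan contains is an undefined case, with the source column and the censoring text pointing in different directions.

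It would also be too strong to say that assessments entered after the stop are lost. Sections 8.1 and 8.7.1 include patients who finished treatment before collection began, so all their data are entered afterwards. The sentence in 8.2 limits the observation period for patients on ongoing treatment, not the date of entry. Progression that prompts a stop would usually be found at or before it.

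Other safeguards may reduce the number affected. Sections 8 and 8.8 provide for continuing data review with queries to sites, and a stop for progression with no PD entry is an inconsistency that could be queried. A later recorded death, for instance within the 28-day safety window in Section 10, turns the patient into a late event. That lessens the bias but does not remove it.

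The shifts are modest against sampling error. With about 33 events, a rough 95% interval around 6 months is 6 × exp(±1.96/√33), or 4.3 to 8.4, which contains the 10% and 20% results. This is a fair comment on precision, but the bias always runs upward, and the interval around the biased estimate would not reveal it.

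Finally, counting a stop as PD mixes a treatment decision with assessed progression, and the stop date may be later than progression if treatment continued beyond it. That is a reason to show both versions. It does not excuse leaving the rule unstated.

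**Conclusion.** The point holds as a missing rule with a predictable direction of bias. The plan does not say whether discontinuation for progression, without a recorded PD assessment, is a PFS or DOR event, or on which date. If the 8.7.5 source column is followed, these patients are censored informatively at about the stop date, or counted late at death, and the result contradicts the disposition table.

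The size cannot be established, because the documents give neither the share affected nor an expected median. The 6.7, 7.5 and 8.6 months are conditional on an assumed 6-month exponential median, on f of 10%, 20% and 30%, and on permanent censoring. Recorded deaths, or any PFS events that are deaths without progression, would make the shift smaller. No hypothesis test is affected, as the study is descriptive (Section 8.7). The change should still be made, because PFS and DOR are reported endpoints and the remedy uses data already collected.

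**What to change.** 1. In 8.7.5, define the PD date for both PFS and DOR as the earlier of (a) the first HCP-reported response of PD and (b) the lorlatinib discontinuation date when the recorded reason is disease progression. Death remains the event when neither is present.
2. In 8.7.6, reword the PFS and DOR censoring rules to use this single definition of progression, in place of the present two descriptions.
3. Report at each milestone how many PFS and DOR events rest on the discontinuation reason alone.
4. Present PFS and DOR with assessment-based PD only as a sensitivity analysis.

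The cost is one derivation line, a wording change and one extra run. Both variables are already in the data collection tool (Section 8.3). The downside is that some clinical, non-imaging progressions will count as events, so PFS and DOR become slightly less favourable. The sensitivity analysis shows by how much.

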8.7.6 Statistical summaries

Demographic and clinical characteristics

The number and percentage of patients will be presented within each categorized variable. In addition, descriptive statistics for continuous variables will include the mean, standard deviation, median, interquartile range, minimum and maximum.

The demographics will also be presented by subgroups for any subgroups with more than 5 patients.

HCP's reported objective response

For each response component (with the exception of best response), the responses will be listed along with the date of the assessment. A derived objective response will be produced and compared to the HCP overall reported response for confirmation of robustness.

Best Overall Response (BOR) and Overall Response Rate (ORR)

For the BOR, the number and percentage of patients in each ordered category will be presented and summarized by baseline disease status. In addition, the ORR will be presented including the Clopper Pearson 95% Confidence interval.

PFIZER CONFIDENTIAL

Duration of response

The number and percentage of patients will be presented within each of the following categories for duration of response: 0 to <3 months; 3 months to <6 months; 6 months to <1 year; 1 to <2 years; 2 to <3 years >3 years; lost to follow-up. Kaplan-Meier (KM) estimates will be used to give the median, Q1 and Q3 duration of response, with 95% confidence limits. If a patient does not show symptoms of progressive disease, their duration of response will be censored at their last visit date prior to the data cut-off date.

Time to event

KM estimates will be presented, where possible, for duration of treatment, progression free survival and overall survival (i.e., time to death). The following censoring rules will be applied:

- Duration of treatment

Patients who have not discontinued treatment at the data cut-off date will be censored based on the last recorded date when the patient was known to be continuing treatment prior to the data cut-off date.

- Progression free survival

Patients who have not experienced PD or died at the data cut-off date will be censored at the date of last contact prior to the data cut-off date.

- Overall survival

[figure not shown]
Any patient not known to have died at the data cut-off date will be censored based on the last recorded date on which the patient was known to be alive prior to the data cut-off date.

The KM curves will be used to estimate the median, Q1 and Q3 survival times, with 95% confidence limits. The proportion of patients with an event will also be estimated from the corresponding Kaplan-Meier curves with 95% confidence limits.

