7. RESEARCH QUESTIONS AND OBJECTIVES

The primary goal of the Pfizer expanded access program is to provide access to lorlatinib to patients with a serious or immediately life-threatening disease/condition who have exhausted all other standards of care and are not eligible for a clinical trial. Treatment is delivered by the healthcare professional (HCP) as sponsor of the expanded access request and according to a treatment plan approved institutional review board/independent ethics committee as required by local laws and regulations or institutional requirements.

The overall goal of this real-world data collection is to assess demographic, clinical characteristics and real-world effectiveness of pediatric neuroblastoma patients who initiated treatment with lorlatinib through an expanded access program. Data will be collected to address the following specific objectives:

1. Describe the demographic and clinical characteristics of pediatric neuroblastoma patients who initiated treatment with lorlatinib through an expanded access program
2. Evaluate the effectiveness of treatment with lorlatinib in pediatric neuroblastoma patients in terms of duration of treatment, HCP reported response, and duration of response
3. Estimate progression free survival and overall survival
4. Collection of safety data

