8.1. Design of data collection

Up to 50 pediatric patients with ALK-aberrant neuroblastoma who initiated treatment with lorlatinib as part of expanded access program will be included.

The real world data collection will be initiated after the patient has been approved for expanded access to lorlatinib per Pfizer's expanded access program and the treating HCP has agreed to participate in data collection. All assessments described in this protocol are performed as part of normal clinical practice or standard practice guidelines for the patient population and healthcare provider specialty in the countries where this data collection is being conducted. Data from patients who have completed treatment, patients receiving ongoing treatment and new patients will be captured. A progress report will be developed for the patients who have completed treatment, with a more comprehensive final report descriptive in nature produced for the total population.

[figure not shown]

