8.7. Data analysis

Bionical Emas in collaboration with Syne Qua Non Limited (SQN) will perform the data analyses described in this protocol using SAS statistical software. Statistical summaries, figures and listings will be produced using SAS (version 9.4 or later).

All development of data summaries and analyses will be documented and retained for traceability including dataset specifications and derivations, name of the programmed outputs and assigned program authors and reviewers.

All data outputs will be fully quality controlled including review of the logs and associated outputs.

No formal statistical testing is planned, and all data analyses will be descriptive and explorative.

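### The duration-of-response censoring sentence in Section 8.7.6 leaves out death, which Section 8.7.5 makes an end point, and should be aligned with it

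*Combined protocol and SAP*

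**What the plan says.** **Definition (Section 8.7.5, DOR row).** The end of the interval is given as "Derived as (Date of PD or death, whichever occurs first", and the start is the first PR or CR. The source named for the endpoint is the HCP-reported response date.

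**Censoring (Section 8.7.6, under the DOR heading).** "If a patient does not show symptoms of progressive disease, their duration of response will be censored at their last visit date", with the last visit taken before the data cut-off. Death is not mentioned. KM median, Q1 and Q3 with 95% limits are to be reported.

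**PFS, for comparison.** The derivation in Section 8.7.5 runs to "Date of PD or death (by any cause in the absence of PD", and the censoring rule in Section 8.7.6 matches it: "Patients who have not experienced PD or died at the data cut-off date will be censored at the date of last contact".

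**Context.** Objective 2 in Section 7 assesses effectiveness "in terms of duration of treatment, HCP reported response, and duration of response". Section 8.7 states: "No formal statistical testing is planned, and all data analyses will be descriptive and explorative". No section says which of 8.7.5 and 8.7.6 prevails where they differ.

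**The concern.** A responder who dies without having shown symptoms of progression satisfies two instructions at once. Under Section 8.7.5 the death ends the response and is an event. Under the words of Section 8.7.6 the patient is censored at the last visit. A programmer has to choose, and the plan does not say how.

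If the censoring sentence is followed to the letter, the same patient appears in one report as a PFS event and as a censored case for DOR. Dropping such deaths from the event count lengthens the estimated DOR, so the error favours the treatment. DOR is one of the three measures in Objective 2, and Section 11 foresees use of the results for regulatory authorities and publication.

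The situation can arise. Section 8.2 expects visits every 3 to 4 months, so a responder may die between assessments. The documents do not say how often this would happen.

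**Working it through.** **1. The two rules side by side**

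| Responder's situation | DOR by 8.7.5 | DOR by 8.7.6, literally | PFS |
|---|---|---|---|
| Dies, no symptoms of progression, no PD date | Event at death | Censored at last visit | Event at death |
| Dies, symptoms of progression, no HCP-reported PD | Event at death | Not covered by the sentence | Event at death |
| Alive, no symptoms, no PD date | No end date | Censored at last visit | Censored at last contact |

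The conflict is confined to the first row. The literal condition concerns symptoms of progression, so it does not catch every death without a recorded PD.

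**2. Is there a figure to reproduce?** No. The plan gives no expected DOR, event count or power calculation. What follows shows scale only.

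**3. Size of the shift, by assumption**

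Let f be the share of first DOR events that are deaths caught by the literal sentence. The documents give no value for f. Assume constant independent hazards with total hazard λ.

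- If these deaths are censored at the death date, the hazard that KM sees is (1 − f)λ.
- Every quantile is then multiplied by 1/(1 − f).
- At the true median, KM would show 0.5^(1 − f) still in response.

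| Assumed f | Quantile multiplier 1/(1 − f) | KM at true median |
|---|---|---|
| 0% | 1.00 | 50.0% |
| 5% | 1.05 | 51.8% |
| 10% | 1.11 | 53.6% |
| 20% | 1.25 | 57.4% |

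**4. Censoring at the preceding visit**

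The sentence censors at the last visit, which may precede death. A simulation of 200,000 responders assumed a 12-month median for PD or death, administrative censoring uniform over 6 to 48 months, and visits 3.5 months apart.

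- f = 10%: median 13.19 against 11.99 months, ratio 13.19/11.99 = 1.10.
- f = 20%: median 14.77 against 12.04 months, ratio 14.77/12.04 = 1.23.

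So 1/(1 − f) is an upper figure under this model, and visit-based censoring gives slightly less.

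**5. Comparison with sampling error**

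Section 8.1 caps the collection: "Up to 50 pediatric patients with ALK-aberrant neuroblastoma". Take the most favourable case, in which all 50 respond and all have an observed event. Under the same exponential model:

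- The large-sample standard error of the log KM median is 1/(ln 2 × √50) = 1/(0.693 × 7.071) = 0.204.
- The 95% limits are exp(±1.96 × 0.204), about 0.67 to 1.49 times the median.

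Shifts of 1.11 and 1.25 both lie inside these limits. Fewer responders or fewer events would widen them.

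**The case against.** The strongest reply is that Section 8.7.5 already settles the matter. On the literal reading of Section 8.7.6, the death clause in the DOR derivation would almost never operate: death after PD is pre-empted by PD, and death without progression is censored. Reading the censoring sentence as covering only patients with no end date gives effect to both sections. This is right as to the more natural reading, and it makes the defect an incomplete sentence more than a rival rule. It does not remove the need for a correction. No precedence is stated, and the PFS wording cannot simply be carried across, because the DOR sentence stands under its own heading before the list of time-to-event censoring rules.

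A reader might infer that the plan sets out to censor deaths, or that every death without recorded PD would be lost from DOR. The documents support neither. The first ignores Section 8.7.5. The second replaces the sentence's condition, symptoms of progression, with a different one.

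It is also fair to say that no effect is demonstrated. With f = 0 nothing changes, the analysis is descriptive, and PFS, which counts death explicitly, is reported alongside. All of this stands and limits the severity.

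**Conclusion.** The DOR censoring sentence is inconsistent with the DOR derivation as written, and it should be corrected. Severity is minor.

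If the sentence is applied literally and at least some responders die without symptoms of progression, KM DOR is biased upward. Under constant independent hazards the multiplier is up to 1.11 at an assumed f of 10% and up to 1.25 at 20%. Both values of f are assumptions, since the documents give none. A reader might take these multipliers as evidence of a material distortion. They are not: even 1.25 lies well within the sampling limits for 50 observed events, so the case rests on a consistent rule and not on a shown numerical effect.

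ORR, PFS and OS are not affected, and no hypothesis test is involved. The correction also leaves untouched any bias from ending follow-up at treatment discontinuation (Sections 8.2 and 9.3), which is present under either rule.

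**What to change.** Replace the DOR censoring sentence in Section 8.7.6 with wording such as:

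> Responders with neither HCP-reported PD nor death by the data cut-off are censored at their last visit before the cut-off; death without PD counts as an event on the date of death.

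This makes two changes, and both should be disclosed:

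1. Death without PD becomes an explicit event, as in Section 8.7.5.
2. HCP-reported PD replaces the undefined reference to symptoms of progression. This agrees with the HCP-reported source that Section 8.7.5 names for DOR. One consequence is that a living responder with symptoms but no HCP-reported PD is censored, a case the present sentence leaves open.

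No new data are needed, because Section 8.3 already lists "last date of lorlatinib, patient alive, date of death" among the variables. The cost is that the reported DOR may be shorter than under the literal rule. If the sponsor already intends death to count, the edit only records that intention.

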8.2.1. Inclusion criteria

Patients must meet all the following inclusion criteria to be eligible for inclusion in the study:

1. Patient treatment with lorlatinib is initiated through Pfizer's expanded access program for treatment of ALK+ neuroblastoma.
2. HCP documentation of at least one tumor assessment of response after patient has had at least one dose of lorlatinib
3. Evidence of a personally signed and dated informed consent document indicating that the patient (or a legally acceptable representative, or a waiver of informed consent has been granted by the IRB/IEC) has been informed of all pertinent aspects of the study.

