9.3. Patient withdrawal

Patients may withdraw from the study at any time at their own request, or they may be withdrawn at any time at the discretion of the HCP or sponsor for safety, behavioral, or administrative reasons. In any circumstance, every effort should be made to document patient outcome, if applicable. The HCP would inquire about the reason for withdrawal and follow-up with the patient regarding any unresolved adverse events.

PFIZER CONFIDENTIAL

If the patient withdraws from the data collection, and also withdraws consent for disclosure of future information, no further evaluations should be performed, and no additional data should be collected. The sponsor may retain and continue to use any data collected before such withdrawal of consent.

Treatment discontinuation or loss to follow-up do not constitute patient withdrawal, date of discontinuation or loss to follow-up will be considered last visit date for that patient.

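### PFS is censored at an undefined last contact and DOR at last visit, not at the last disease assessment, so any unassessed time counts as progression-free

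*Combined protocol and SAP*

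**What the plan says.** Section 8.7.5 defines the PFS event as progression or death: "Derived as (Date of PD or death (by any cause in the absence of PD)) – (Treatment start date) + 1". DOR ends at the same events, counted from first CR or PR.

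Section 8.7.6 gives the two endpoints different censoring dates. For PFS, patients with neither event "will be censored at the date of last contact prior to the data cut-off date". For DOR, a patient without progression has "their duration of response will be censored at their last visit date prior to the data cut-off date". Section 9.3 then adds, for stopping treatment or being lost: "date of discontinuation or loss to follow-up will be considered last visit date for that patient". Last contact is not defined anywhere.

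On how often disease is assessed, section 8.2 says "Visits are anticipated to occur every 3-4 months, corresponding with re-supply of lorlatinib" and leaves the timepoints to local practice. Section 8.2.1 requires only "HCP documentation of at least one tumor assessment of response after patient has had at least one dose of lorlatinib". Section 8.7.5 has the response items entered at each visit, and section 8.3 lists the assessment date as a collected variable.

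On how long patients are followed, section 8.2 ends collection at treatment discontinuation, death, loss to follow-up or study end, whichever is first. Section 10 requires a safety reporting period of at least 28 days after the last dose.

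**The concern.** A patient who is in contact but not assessed cannot be recorded as progressing, yet stays in the risk set as progression-free. Among censored patients this error has one direction: the Kaplan-Meier curve is held up.

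Nothing in the plan ensures that each contact carries an assessment. Visits follow drug re-supply, assessments follow usual care (section 8.1), and scans done outside the treating centre are unavailable (section 8.9). Patients who finished treatment before January 2021 are included (section 8.7.1), and the first was treated in March 2017 (section 8.2). Their charts may hold contact dates later than their last assessment. Because section 9.3 sets the last visit at the discontinuation or loss date whether or not disease was assessed then, DOR is exposed too.

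PFS is part of objective 3, there is no comparator to share the bias, and section 6 notes that such data may supplement regulatory submissions. No missed-assessment rule, sensitivity analysis or listed limitation covers the point.

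**Working it through.** The plan states no PFS figure, event count or power, so there is nothing to reproduce. The check asks which way the rule pushes the result, and by how much under stated assumptions.

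**Mechanism by hand.** For exponential times, median = ln 2 × total follow-up / events. Assume 50 patients (the maximum in section 8.1), 400 patient-months up to last assessment and 20 events: 0.693 × 400 / 20 = 13.9 months. Give each of the 30 censored patients 3.5 months of unassessed contact: 0.693 × (400 + 30 × 3.5) / 20 = 0.693 × 505 / 20 = 17.5 months. With no gap, the two rules coincide. This shows direction only.

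**Simulation.** From the documents: visits 3-4 months apart; safety contact of 28 days after the last dose. Assumed: median time to progression 6 months; median 10 months from progression to death; cut-off 6-60 months after start; 30% of patients stop without progression, at a time uniform over 0.5-18 months. The first visit is always scanned, in line with the inclusion criterion. Progression is dated at the visit that finds it. Both rules are applied to the same simulated patients. The reference is scanning at every visit with no drop-out; it does not depend on the stopping pattern, so the value in row A also serves row D.

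12-month PFS:

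| Scenario | Reference | Last contact | Last assessment |
|---|---|---|---|
| A. Contact ends 28 days after stopping, every visit scanned | 0.296 | 0.294 | 0.276 |
| B. As A, 30% of later visits unscanned | 0.294 | 0.342 | 0.307 |
| C. As A, half of later visits unscanned | 0.297 | 0.387 | 0.340 |
| D. Contact 6-24 months after stopping, every visit scanned | 0.296 | 0.336 | 0.287 |

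Error of the last-contact rule: A, 0.294 − 0.296 = −0.002; B, 0.342 − 0.294 = +0.048; C, 0.387 − 0.297 = +0.090; D, 0.336 − 0.296 = +0.040. In C the medians are 7.3 months (reference), 9.9 (last contact) and 7.8 (last assessment).

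Not all of the error in C comes from the censoring date. The part that changes with the rule is 0.387 − 0.340 = 0.047. The remaining 0.340 − 0.297 = 0.043 arises because missed scans delay detection of progression, and no censoring rule removes that.

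**Error of the alternative rule.** In A, last-assessment censoring is low by 0.296 − 0.276 = 0.020; with 15% stopping it gives 0.281, low by 0.015. A separate simulation assumed a median time to progression of 12 months, with 20% of patients per visit ceasing to be assessed. Full assessment gives a median of 13.5 months. With 3.5 months of further contact, last contact gives 14.3 (+0.8) and last assessment 11.2 (−2.3). With 7 months, the figures are 16.3 (+2.8) and 11.0 (−2.5). The rule reads low because deaths in the gap count as events while death-free gap time is dropped.

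**The case against.** The strongest reply is that the plan leaves little room for a gap. Response is to be recorded at each visit, collection stops at discontinuation, and the only planned extension is the safety period. Scenario A is that plan, and there the existing rule is nearly unbiased while the proposed rule is the more biased of the two. The analysis is descriptive, and at 50 patients a 12-month PFS of 0.30 has a 95% half-width of about 1.96 × √(0.30 × 0.70 / 50) = 0.13, larger than any error in the table. All of this stands, and it makes the claim conditional. It does not remove it: recording a response field at each visit does not mean that disease was imaged, and B and C show the bias within the planned follow-up window.

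Three stronger readings are tempting and not supported.

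- A reader might infer that PFS is certainly inflated, picturing a patient scanned at month 2 and in contact at month 24. The single post-dose assessment is an entry criterion, not the schedule, and planned collection would not normally produce that record.
- A reader might take "every effort should be made to document patient outcome" to mean that outcome is pursued long after stopping. That sentence concerns withdrawal; section 9.3 says discontinuation is not withdrawal and fixes the last visit at the discontinuation date, which limits the window.
- A reader might infer that last-assessment censoring is close to unbiased. The 11.0 and 11.2 against 13.5 months above show otherwise.

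The DOR part is weaker than the PFS part, because its date is a visit at which response should be recorded.

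**Conclusion.** The concern holds conditionally. As written, the rule lets unassessed time count as progression-free, with an undefined date for PFS and a different one for DOR although both share the same end events. How much this matters depends on the gap between last assessment and last contact, which the documents do not give. The effect on 12-month PFS is near zero if the plan is followed strictly, and about +4 to +9 points in scenarios B to D. Those figures rest on the assumed 6-month median, the 30% stopping and the chosen gaps; they are scenario values, not predictions. What is affected is the reported medians and Kaplan-Meier proportions. No hypothesis test is planned, so type I error is not in question.

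**What to change.** In section 8.7.6:

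- Censor PFS and DOR at the last response assessment without progression (day 1 for PFS if there is none).
- State how progression or death after a gap in assessments is handled.
- Define last contact, and report PFS under that rule as a sensitivity analysis beside the main result.
- Report the distribution of the gap between last assessment and last contact.
- Keep the last-known-alive date for OS only.
- State that the last visit date of section 9.3 does not set the PFS or DOR censoring date.

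The cost is a wording change and one repeat Kaplan-Meier run; no new data item is needed for the main rule. The downside is a modestly conservative PFS, about 1-2 points at 12 months when scanning is complete and more with heavy assessment drop-out. That is the reason to show both results.
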